6 STUDY INTERVENTION(S) OR EXPERIMENTAL MANIPULATION(S)

6.1 STUDY INTERVENTION(S) OR EXPERIMENTAL MANIPULATION(S) ADMINISTRATION

6.1.1 STUDY INTERVENTION OR EXPERIMENTAL MANIPULATION DESCRIPTION

Person-family dyads assigned to both the intervention and control groups will receive usual care, comprising standard primary care at participating practices. Usual care involves following patients at variable intervals, with routine visits scheduled at 2 weeks-6 months, depending on the stability of health status. All patients may register for the patient portal, provide their primary care clinician / clinic with a completed advance directive to be uploaded in their electronic health record, or avail themselves of advance care planning with their primary care clinician or other clinic staff. However, these processes generally occur on an ad-hoc basis and do not involve a protocolized approach to engaging with family caregivers or advance care planning.

Person-family dyads assigned to the control group will receive a protocol of minimally enhanced usual care, encompassing an introductory letter (**F1B**), a print educational brochure (**F6**) and blank easy to complete advance directive (**F4, F5**). The educational materials include a 44-page brochure developed by the National Institute on Aging entitled “A Guide for Older People: Talking with your Doctor” (**F6**)⁶¹ and an easy-to-read advance directive (**F4, F5**). Control dyads will be told that they are participating in a study about communication in primary care. We chose an active control arm for several reasons: 1.) because providing an advance directive should be the standard of care even if it is often not ‘usual care’, 2.) to ensure that positive results can be attributed to the effectiveness of the intervention, and 3.) to mitigate perceptions among dyads randomized to the control group that they are not being offered anything beyond usual care.

Person-family dyads assigned to the intervention protocol will receive usual care in addition to SHARE, encompassing the following four components (see exhibit below).

1. An invitation from the primary care clinic introducing the intervention to prepare patients and families to engage in advance care planning discussions (**F1A, F7**),²⁴
2. Access to an ACP facilitator/ interventionist trained in the protocol and leading advance care planning for persons with cognitive impairment and their families,^{26,27}

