9 STATISTICAL CONSIDERATIONS

9.1 STATISTICAL HYPOTHESES

Objectives and hypotheses related to primary outcomes are as follows:

We test the efficacy of SHARE on quality of communication (primary outcome) and advance care planning processes (secondary outcomes) at 6 months among primary care patients with cognitive impairment (mild-severe) and family caregiver dyads. We hypothesize that as compared with the control group, caregivers in the intervention group will report better quality of communication about end of life care with primary care clinicians at 6 months (primary outcome).

Objectives and hypotheses related to secondary outcomes are as follows:

We further test the efficacy of SHARE on advance care planning processes at 6 months. We hypothesize that intervention caregivers will be more highly engaged in advance care planning than control caregivers as measured by caregiver-reported readiness to engage in advance care planning and having documented advance directive in the patient's electronic health record at 6 months. We expect patient-reported outcomes will mirror those reported by caregivers and that outcomes will be achieved without adversely affecting the therapeutic alliance with the primary care clinician or perceptions of shared decision-making with the primary care team.

For patients who die by 24 months, we examine quality of end of life care and bereaved family caregiver experiences with medical decision-making. We hypothesize caregivers in the intervention group will report higher quality of end-of-life care than those in the control group as measured by the Satisfaction with Care at the End-of-Life in Dementia scale. We expect that bereavement outcomes will be superior among intervention caregivers than control group caregivers as measured by less decisional conflict, less decisional regret, and fewer symptoms of anxiety and depression. Finally, we expect that decedents in the intervention group will be less likely to experience burdensome care at the end of life than decedents in the control group.

We expect patient-reported outcomes will mirror those reported by caregivers and that outcomes will be achieved without adversely affecting the therapeutic alliance with the primary care clinician.

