9.3 POPULATIONS FOR ANALYSES

The populations for analyses encompass a sample of about 248 person-family dyads who meet eligibility criteria specified in Section 5 of this protocol. The table below summarizes information that will be assessed from patient and family participants.

| 9.3 Table of Assessments | | | | | | | | | | | | |
|---|---|---------------------------------|-------|--------------------------------|------------|-------------|----|----|-----|-----|-----|--|
| Construct | Measure | Items | Range | Validity | Source | Outcome | BL | 6M | 12M | 24M | EOL | |
| Outcomes @ 6 Months, Patient and Family Experience | | | | | | | | | | | | |
| QOC (Primary) | Quality of EOL Communication ^{51,84-87} ; General QOC Subscale and Global (Secondary) | 7 7 | 0-70 | $\alpha=0.79$ $\alpha=0.91$ | P, F | F@6M | X | X | X | X | | |
| ACP (Secondary) | Sudore 4-item ACP engagement μ ^{88,89} | 4 | 0-20 | $\alpha=0.84$ | P, F | F@6M | X | X | X | X | | |
| | Advance Directive Completion ²⁰ | -- | Y/N | -- | EMR | E@6m | | X | X | X | X | |
| Outcomes @ EOL, Quality of Care and Surrogate Decision-Making Experience | | | | | | | | | | | | |
| Quality of EOL (Primary) | Satisfaction w/ Care at the EOL in Dementia ^{51,90} | 10 | 10-40 | $\alpha=0.90$ | F | F@EOL | | | | | X | |
| Surrogate Decision- Making (Secondary) | Decisional conflict scale ⁹¹⁻⁹³ | 16 | 0-100 | $\alpha=0.78$ | F | F@EOL | | | | | X | |
| | Decisional regret – Brehaut ⁹⁴⁻⁹⁶ | 5 | 0-100 | $\alpha=0.81-0.92$ | F | F@EOL | | | | | X | |
| | Anxiety: GAD-7 ^{97,98} | 7 | 0-21 | $\alpha=>0.92$ | F | F@EOL | X | X | X | X | X | |
| EOL care (Secondary) | Burdensome care | | | | EMR/F | EMR@ EOL | | | | | X | |
| Primary Care Interactions and Communication | | | | | | | | | | | | |
| Therapeutic alliance | Human Connection Scale ⁹⁹⁻¹⁰³ | 16 | 16-64 | $\alpha=0.90$ original | F | - | X | X | X | X | | |
| Shared Decision- Making | CollaboRATE μ ¹⁰⁴⁻¹⁰⁷ | 3 | 0-100 | $\alpha=0.89$; 0-9/item | P, F | - | X | X | X | X | | |
| Primary Care Interactions | Frequency/Mode of Contacts ^{29,108,109} (IH) | 5 | -- | Homegrown | F, E | - | X | X | X | X | X | |
| | Use of patient portal | -- | -- | -- | EMR | - | X | X | X | X | X | |
| Implementation, Fidelity/Implementation Processes, Clinic Context (Note: these items will be limited to intervention participants) | | | | | | | | | | | | |
| Acceptability | Acceptability: Recruitment & retention | Consort diagram | | | | - | | | | X | | |

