For dichotomous outcomes (e.g., newly documented advance directive; burdensome care) we will construct multilevel logistic regression models using SAS Proc GLIMMIX. We will compute the effect size of primary and secondary outcomes to assess SHARE effects relative to other treatment effect estimates for advance care planning interventions reported in the published literature. The multilevel model will also be used to examine potential intervention moderation effects by examining two-way interaction effects between intervention (SHARE vs. control) and either dyad (e.g., cognitive impairment, caregiving relationship) or clinic characteristics (e.g., size, urban vs. suburban/rural) in separate models. Given the relatively modest sample size available for some secondary analyses, careful attention must be given to potential problems such as over-parameterization; thus only a limited number of covariates will be included in these models and potential interactions will be examined in separate models. We will examine rates of recruitment and retention, the timeliness and completeness of collected data,¹³⁰ and relative attrition rates (SHARE versus control protocol).⁶⁰

Qualitative Strand. At the end of the study, we will assess the acceptability of SHARE and the mechanism of observed effects.^{131,132} From audio-recordings of advance care planning facilitation sessions we will examine the duration, content, and receptivity to components of SHARE. After the completion of 24-month interviews or at any point after enrollment, we will seek invite select group of 12-20 dyads, all ACP facilitators and ACP fidelity raters to complete post-intervention in-depth interviews. These interviews will be audio-recorded, transcribed verbatim, and entered into NVivo 9 textual data analysis software. Qualitative analyses will be conducted by the study team concurrent to data collection using a framework approach^{132,133} involving familiarization with content, identification of a thematic analytic framework, data indexing, charting to abstract and distill key themes, and the mapping of charts to interpret themes and context-specific meaning. We will ensure rigor and minimize bias by comprehensively documenting data collection, regular study team debriefs, triangulation of diverse stakeholder perspectives and data

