2. **Documentation of advance directive completion in the electronic health record** is defined as having a durable power of attorney or a living will documented in the primary care electronic health record.^{51,144,145} We do not consider the Medical Order for Life Sustaining Treatment (MOLST) in inclusion/exclusion criteria for the study or as an outcome of advance directive completion as the completion of a Maryland MOLST is mandatory in certain situations (e.g., on transfer between settings of care) and is not indicative of having had an advance care planning discussion or naming a durable power of attorney; the Maryland MOLST does not conform to the National POLST Paradigm.^{146,147}

Bereaved Family Caregiver Experiences. Among patients who die by 24 months, we assess 4 secondary outcomes relating to bereaved caregiver experiences with medical decision-making and burdensome care among older adults as follows.

1. **Decisional conflict.** The Decisional Conflict Scale is a 16-item instrument scored on a 5-point Likert scale ranging from 1 to 5.⁹¹ Aggregate scores range from 0 (no conflict) to 100 (extremely high conflict).⁹¹⁻⁹³
2. **Decisional regret** will be assessed using a 5-item instrument that assesses the extent to which decision-makers experience regret about care. Response options are assessed using a 5-item Likert scale in which scores of 1 indicate the least regret and 5 the most regret. Scores are then reduced by 1 point and multiplied by 25 for a scale that ranges in value from 0 to 100. Prior studies have categorized scores of 0 as no regret, 1 to 25 as mild regret, and more than 25 as heightened regret.⁹⁴⁻⁹⁶
3. **Symptoms of anxiety.** The Generalized Anxiety Disorder 7-item (GAD-7)⁹⁷ is a validated instrument that ask about symptoms of anxiety using a two-week recall period with response categories that vary from 0 ("not at all") to 3 ("nearly every day"). Item responses are summed to construct composite scores.
4. **Burdensome care.** Burdensome care will be measured by any intensive care unit use or life prolonging care (cardiopulmonary resuscitation, mechanical ventilation, tracheostomy, dialysis, artificial nutrition, chemotherapy) within 30 days of death^{101,102} using dates and services abstracted from medical records and the Chesapeake Regional Information System (CRISP), Maryland's Health Information Exchange, which includes all hospital encounters.

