10.1.9 DATA HANDLING AND RECORD KEEPING

10.1.9.1 DATA COLLECTION AND MANAGEMENT RESPONSIBILITIES

To minimize participant burden and disruption to primary care practices, the study team will obtain oral informed consent (**B4, C2, D4**) and conduct a written or electronic baseline survey (**B6, C3**) prior to randomization. Contextual information about how oral consent is obtained will be stored in REDCap. Follow-up and bereavement assessments will be conducted by telephone and web survey via by study staff masked to treatment group (**C7**). Follow-up and bereaved assessments obtained via web survey will be stored in REDCap. Measures of advance directive completion, use of the patient portal, and burdensome care will be extracted from the electronic health record and the Maryland CRISP by study staff masked to treatment group. Data collection will be the responsibility of research staff under the supervision of the research program manager and primary investigator.

All data will be maintained in confidentiality, and confidentiality protections will be included in study staff research training. Data collection will employ standardized data forms. Data from screening calls, intervention contacts and participant surveys will be entered into REDCap forms that the data manager will check for completion and accuracy. The data manager will provide semi-monthly reports of missing or inappropriate entries to the PI for clarification and resolution. Standardized electronic data validation checks will be developed within the database constructs using data entry discrepancy flags, programmed query rules, and in certain cases, external rules using SAS code. Monthly reports in aggregate and by study site will be generated summarizing accrual, completeness of follow-up, and study withdrawals. Periodic reports will be generated at the request of the Project Manager or the Principal Investigator. The Data Manager will generate all these reports, working collaboratively with the Biostatistician and study staff. The study database will comply with current data security standards, provide real-time data entry validation, and provide audit trails documenting changes or corrections of the study data. Data entry or review will require logging into a secure portal with a username and password. The database is hosted by the Johns Hopkins Bloomberg School of Public Health and is HIPAA-compliant.

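### The advance-directive secondary outcome is worded both as status on file at 6 months and as a new directive, and Table 9.3 schedules no baseline value to connect the two

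*Combined protocol and SAP*

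**What the plan says.** - **Definition.** Section 9.4.3 says the outcome "is defined as having a durable power of attorney or a living will documented in the primary care electronic health record". It sets no condition on when the document was filed.
- **Time point.** The hypotheses in Sections 3.2 and 9.1 refer to a directive in the "electronic health record at 6 months". The Table 9.3 row is yes/no, with the record as source and 6 months as the outcome time. Together with the definition, this is status on file at 6 months.
- **Model.** Section 9.4.1 gives two examples of dichotomous outcomes: "newly documented advance directive; burdensome care) we will construct multilevel logistic regression models using SAS Proc GLIMMIX". It states no reference date for new and no rule for directives already on file.
- **Schedule.** In Table 9.3 the advance-directive row is marked at 6, 12 and 24 months and at end of life, and its baseline cell is empty. Portal use, from the same source, does have a baseline mark: "Use of patient portal | -- | -- | -- | EMR | - | X".
- **Extraction.** Section 10.1.9.1 states: "Measures of advance directive completion, use of the patient portal, and burdensome care will be extracted from the electronic health record". It gives no look-back date. For burdensome care, Section 9.4.3 does specify "using dates and services abstracted from medical records"; the directive item has no such wording.
- **Eligibility and usual care.** Nothing in Sections 5.1 or 5.2 excludes a patient who already has a directive. Under Section 6.1.1 any patient may "provide their primary care clinician / clinic with a completed advance directive to be uploaded in their electronic health record", so signing date and filing date can differ.
- **Use of the result.** Section 9.4.1 adds: "We will compute the effect size of primary and secondary outcomes to assess SHARE effects relative to other treatment effect estimates".

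**The concern.** Status at 6 months and a new directive by 6 months are different quantities unless nobody has a directive at entry. A patient with a long-standing directive is a yes under the definition. Under the modelling wording the same patient could be a no, could be left out of the denominator, or could be a yes if a further document is filed. The plan does not choose between these, so an analyst could choose after seeing the data.

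The choice affects two things. First, patients who already have a directive count as yes in both arms under the status definition, and this dilutes the contrast. Second, the odds ratio to be set beside published estimates changes with the definition, so a reader has to know which one is reported. A baseline value would let the analysis deal with prior directives, but none is scheduled.

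**Working it through.** **1. Figures in the plan.** The documents give no rate, sample size or power for this outcome. The only power claim for a binary outcome is in Section 9.2: burdensome care, 124 observations, 30% against 10%, more than 80%. The pooled two-proportion formula below, with 62 per arm, gives 0.803. It agrees with the plan and is used for the rest.

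Power = Φ{ (|p1 − p2| − 1.96·√[2p̄(1 − p̄)/n]) / √[(p1(1 − p1) + p2(1 − p2))/n] }, with p̄ the mean of p1 and p2 and n per arm.

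**2. Inputs.** From the plan: 124 per arm (248 dyads, 1:1) and a two-sided 0.05 test (stated for the primary outcome). Assumed, for illustration only: among patients with none on file, 15% of controls and 35% of SHARE patients file a directive by 6 months; a share π of 10, 20 or 30% has a prior directive; prior directives persist. Section 2.3.3 says only that completion of advance care planning is low. No attrition is applied.

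**3. Three readings.** Let c and t be the uptake rates among those with none on file.

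- Status in all randomized: π + (1 − π)c against π + (1 − π)t. The risk difference is (1 − π)(t − c).
- New directive in all randomized, prior holders counted as no: (1 − π)c against (1 − π)t. The risk difference is the same, but the proportions are lower and so is the variance.
- New directive among those with none on file: c against t, on n(1 − π) per arm.

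**4. Numbers at π = 0.30.**

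- Status: 0.30 + 0.70 × 0.15 = 0.405 against 0.30 + 0.70 × 0.35 = 0.545. The difference is 14 points and the odds ratio (0.545/0.455)/(0.405/0.595) = 1.76. The power argument is (0.140 − 1.96 × 0.0634)/0.0628 = 0.25, so power is 0.60.
- New, all randomized: 0.105 against 0.245. The odds ratio is (0.245/0.755)/(0.105/0.895) = 2.77. The argument is (0.140 − 1.96 × 0.0483)/0.0474 = 0.96, so power is 0.83.
- New, none on file: 0.15 against 0.35 on 124 × 0.70 ≈ 87 per arm. The odds ratio is (0.35/0.65)/(0.15/0.85) = 3.05. The argument is (0.200 − 1.96 × 0.0657)/0.0640 = 1.11, so power is 0.87.

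**5. Across prior shares, same uptake.**

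| Prior share | Status: OR, power | New, all randomized: OR, power | New, none on file: OR, power |
|---|---|---|---|
| 10% | 2.31, 0.86 | 2.95, 0.93 | 3.05, 0.94 |
| 20% | 1.96, 0.73 | 2.85, 0.89 | 3.05, 0.91 |
| 30% | 1.76, 0.60 | 2.77, 0.83 | 3.05, 0.87 |

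**6. Sensitivity.** With uptake 10% against 25% and 30% prior, the same formulas give 0.39, 0.72 and 0.74 for the three readings. With 20% against 35% they give 0.38, 0.55 and 0.60. A simulated random-intercept logistic model (9 clinics, assumed intraclass correlation 0.03, uptake 15% against 35%) gave 0.87/0.74/0.58 for status and 0.95/0.92/0.88 for none on file at 10/20/30% prior. Allowing for clinics therefore barely changes the picture.

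**7. Baseline status as a covariate.** If every patient with a prior directive is still a yes at 6 months, the coefficient for baseline status diverges, and those patients add nothing to the likelihood for treatment. In simulated single-level fits (248 patients, 30% prior) the all-patient model with the covariate and the model restricted to none on file gave the same treatment result, for example log odds ratio 1.588, standard error 0.434 and likelihood-ratio statistic 15.86 in both.

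**The case against.** The other side is substantial. The wording newly documented appears once, as an example in a general modelling sentence, while the definition, both statements of the hypothesis and the table agree on status. Section 9.4.1 also says that all participants are analyzed in their assigned group, so the natural reading of the modelling phrase is a new directive among all randomized. On the illustrative rates that reading already brings most of the gain over status (0.83, against 0.87 for the restricted set, at 30% prior). The schedule is not wholly silent either: Section 1.3 marks patient and family experiences at enrollment, and Section 9.4.3 places the directive in that group. Section 8.1 refers to a Manual of Procedures that is not among the documents reviewed.

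Much of this stands and limits the point to a clarification with a modest gain. It does not settle the matter. The intention-to-treat sentence fixes the arm but says neither from which date a directive is new nor how one already on file is scored. Section 1.3 defers to Section 9 for the measures. There the baseline cell is blank, and the baseline list in Section 8.1 names quality of communication and engagement in advance care planning but not the directive.

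A reader might infer more than the documents support:

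- *That the status comparison is biased.* It is not; it compares randomized groups as assigned.
- *That the missing baseline value loses the power for good.* A dated record pull could identify directives on file at randomization after the fact. The plan simply does not say that dates are taken.
- *That the two wordings always classify prior holders in opposite ways.* A prior holder who files another document could be a yes under both, and a restricted denominator would leave that patient out.
- *That a baseline covariate fails because of separation.* Step 7 of the working shows that the treatment estimate is unharmed; software may warn about convergence.

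**Conclusion.** The point holds as an inconsistency in a secondary outcome that is worth correcting. The plan defines and hypothesizes a directive on file at 6 months, models a new one without a reference date or a rule for existing directives, and schedules no baseline value although prior holders are eligible. The shrinkage of the status risk difference by (1 − π) follows for any uptake rates, provided prior directives persist. The power and odds-ratio figures are illustrations on assumed uptake and prior share. At 10% prior, which may fit the plan's remark on low completion better, power is 0.86 for status against 0.93 or 0.94 for the other two readings. The gap is wider at 30%. The plan makes no power claim for this outcome, and the primary outcome and sample size are untouched.

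**What to change.** 1. **Table 9.3.** Add a baseline mark for the advance directive, taken as a dated field (filing date in the primary care record) within the extraction already planned in Section 10.1.9.1. A retrospective dated pull is enough.
2. **Sections 9.4.1 and 9.4.3.** Name one main analysis and word it the same way in both places: directive filed in the primary care record after randomization and by 6 months, in the planned multilevel logistic model, among patients with none on file at randomization. That group is fixed at baseline, so the randomized comparison holds. A model of 6-month status in all randomized patients, adjusted for baseline status, is an equivalent choice if all prior directives persist.
3. **Supporting result.** Report status on file at 6 months by arm in all randomized patients, which answers the hypotheses in Sections 3.2 and 9.1 as written.

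The cost is one dated field and a few words, with no extra patients or contacts. The main analysis uses fewer patients (about 87 instead of 124 per arm at 30% prior), which the power figures above already allow for.
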